**9.1.8 Incident**

The Medical Device Directive (MDD) article 10 and MED DEV defines an incident as: any malfunction or deterioration in the characteristics and/or performance of a device, as well as any inadequacy in the labelling or the Instructions for use which, directly or indirectly, led to or might have led to the death of a subject, or USER or of other persons or to a serious deterioration in their state of health (see definition of SAE).

As per applicable Medical Device Guidance Document, MEDDEV 2.12-1 rev. 8, all events that the Sponsor determines fulfil the criteria of incidence must be reported to applicable Competent Authorities (CAs).

**9.2 PROCEDURE FOR REPORTING ADVERSE EVENTS**

All AEs and ADEs-must be recorded in source documents and on the appropriate eCRF. All AEs that are related and unexpected (not listed as treatment-related in the current package insert or Directions for Use) must be reported as required by the ethics committee, local regulations, and the governing health authorities.

**9.2.1 Timelines for Reporting**

The Investigator is to adhere to the following schedule (*Table 9.1*) in reporting different types of AEs.

**Table 9.1 Adverse Events Reporting Timelines**

Adverse Event Type	Reporting to Allergan	Start of Collection	End of Collection
AEs, ADEs	Record on AE eCRF upon awareness for review by the Clinical Monitor	Immediately after IC signed	last subject visit

Clinical Study Protocol: CMO-MA-FAS-0512

SAEs, SADEs	Record on SAE Form and fax / e-mail to Allergan within 24 hours of awareness	Immediately after IC signed	30 days after last subject visit
-------------	------------------------------------------------------------------------------	-----------------------------	----------------------------------

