## **3 STUDY DESIGN**

[figure not shown]
This is a prospective, open-label, multi-centre, interventional, medical device, post-marketing study evaluating the effectiveness of Juvéderm® VOLIFT™ with Lidocaine for lip augmentation. Subjects will attend up to 7 visits: Screening, Initial Treatment, Day 14 (Touch-up, if required), Day 30, Month 3, Month 6, and Month 12. (Study Exit) (see *Figure 3.1*). 60 subjects will be enrolled.

Eligible subjects will undergo treatment with Juvéderm® VOLIFT™ with Lidocaine administered via injection for enhancement as per the current DFU. Fourteen days after the initial treatment, subjects will return to the clinic and the Investigator will assess the effectiveness of treatment. If the Investigator judges that optimum correction has not been achieved, an optional Touch-up treatment may be performed during the Day 14 visit.

Subjects who receive Touch-up treatment at the Day 14 visit will attend their Day 30 visit 30 days after their last treatment (ie, after Touch-up). Similarly, subsequent follow-up visits for those subjects who undergo Touch-up treatment will occur at 3 and 6, and 12 months after the last treatment received.

At 12 months the subject will return to clinic and carry out all assessments. If eligible for treatment as per the VOLIFT Directions For Use and have had no other treatments / medications as described in the Inclusion / Exclusion since 6 months, the subject will be offered a free retreatment injection of Juvéderm® VOLIFT™ with Lidocaine. If the decision is made to not retreat at 12 months, but a later retreatment is planned, then the subject can be treated outside the study with free treatment.

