**9.1.7 Injection Site Reaction (ISR)**

ISRs following treatment with dermal fillers include redness, pain after injection, tenderness to touch, firmness, swelling, lumps/bumps, bruising, itching, discoloration, and other specified events. Subjects will maintain a diary record of the presence, location, frequency, severity, and duration of any ISR for 30 days after treatment (initial and Touch-up). (See *Section 7.1.7: Injection Site Reaction (ISR) 30-Day Diary* for further details).

ISRs that persist longer than 30 days (i.e., ongoing at the end of the diary period) will be reported as AE and followed as described in *Section 9.2: Procedure for Reporting Adverse Events*. If an ISR is ongoing or appears 30 days after the patient’s last study visit, it will be followed up by Allergan Product Surveillance separate from this study protocol.

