### 6.2. Key Definitions

A subject is considered 'entered' into the study after the subject has signed the Informed Consent Form (ICF) and a subject number has been assigned.

A subject is considered 'enrolled' after confirmation of participation eligibility and treatment with the investigational product Juvéderm® VOLIFT™ with Lidocaine has occurred during the study.

Study treatment is defined as initial or touch-up treatment with Juvéderm® VOLIFT™ with Lidocaine.

Baseline is defined as the latest assessment prior to any study treatments for each subject.

Study day will be calculated as (date of event or assessment)-(date of first filler treatment)+1 if the event or assessment was on or after the date of the first filler treatment, and as (date of event or assessment)-(date of first filler treatment) if the event or assessment was before the date of the first filler treatment. The day of first filler treatment is Study Day 1 (Visit 1). If a touch-up treatment is administered, Visits 3, 4, and 5 will be 14 days +/- 3 days later than the visit label and window, e.g. the study day for an assessment at Visit 3 (Day 30) could be 44 +/- 10, rather than 30 +/- 7.

End of study is the last clinical visit an enrolled subject has in this study. For subjects who complete this study, the end of study visit will be their Visit 5; for subjects who drop out early, they will be asked to come back for the last clinical visit for end of study data collection.

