### **9.1. Extent of Exposure**

Subject study product exposure will be summarized using descriptive statistics, separately for each treatment visit and overall for the SS, ES, and PPS. At Visit 1, gauge of cannula used and local anesthetic administered will be summarized using descriptive statistics for categorical data, and total volume administered for this treatment (in mL) will be summarized using descriptive statistics for continuous data. At Visit 2, the number and percentage of subjects receiving touch-up treatment will be presented, and for those subjects, gauge of cannula used and local anesthetic administered will be summarized using descriptive statistics for categorical data, and total volume administered for this treatment (in mL) will be summarized using descriptive statistics for continuous data. At Visit 6, the number and percentage of subjects receiving optional retreatment will be presented, and for those subjects, gauge of cannula used and local anesthetic administered will be summarized using descriptive statistics for categorical data, and total volume administered for this treatment (in mL) will be summarized using descriptive statistics for continuous data. Overall, the total volume administered to each subject (in mL) will be summarized using descriptive statistics for continuous data.

The total volume administered to each subject (in mL) will also be summarized using descriptive statistics for continuous data by presence or absence of an AE for the SS.

Scatter plots of total volume administered to each subject (in mL) vs. FACE-Q score by visit will be presented for the SS with the Pearson correlation coefficient calculated for each visit, separately for each gender and overall.

Treatment administered or reason not completed, date of injection, gauge of cannula used, number of filler syringes used, injection technique(s) used during administration, total volume administered (in mL), and local anesthetic administered will be listed for each subject visit for the SS.

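### Non-serious AE collection closes at the Month 12 visit where retreatment is given, yet on the natural reading that volume enters the SAP's volume-by-AE table

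*Protocol*

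**What the plan says.** Protocol Section 3 makes Month 12 the study exit. After the Month 12 assessments, if eligible, "the subject will be offered a free retreatment injection". The protocol treats this injection as part of the study: Section 4.4.2.3 gives post-injection restrictions for retreatment at V6, Section 7.1.5 requires a pregnancy test before it, and Section 8.2.1 refers to study retreatment.

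Table 9.1 ends collection of AEs and ADEs at the "last subject visit" and collection of SAEs and SADEs "30 days after last subject visit". Section 9.1.7 has subjects keep the ISR diary "for 30 days after treatment (initial and Touch-up", the bracket naming no other injection; SAP 9.5 repeats that scope.

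SAP 9.1 plans exposure summaries for Visits 1, 2 and 6: "At Visit 6, the number and percentage of subjects receiving optional retreatment will be presented", together with the volume given. It then plans an overall total volume per subject, and then a summary of total volume "by presence or absence of an AE for the SS" (Table 14.3.4.4). SAP 6.2 reads differently: "Study treatment is defined as initial or touch-up treatment".

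**The concern.** Two things do not fit together.

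First, an injection is given inside the study at the visit that closes non-serious AE collection, and the diary used for the other injections is not extended to it. The directions for use in Protocol Appendix 1 say that side effects may be immediate or delayed, that inflammatory reactions may last a week, and that injection into mucous membrane may cause more oedema and bruising. Most of that period falls after the subject has left V6.

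Second, the SAP appears to count the retreatment volume as exposure in a table that compares volume between subjects with and without an AE. Volume added after the observation window has almost closed can hardly change AE status, but it does change the volume. A reader of Table 14.3.4.4 would take it as evidence on whether more product goes with more AEs, and it would be distorted evidence.

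**Working it through.** The plan states no figure on this point, so there is none to reproduce. The check sets the collection windows side by side, asks what enters total volume, and then shows the form of the effect.

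**1. Collection windows in the visible text**

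| Data | After initial or touch-up injection | After V6 retreatment |
|---|---|---|
| ISR diary | 30 days (Protocol 9.1.7, SAP 9.5) | none described |
| Non-serious AEs, ADEs | up to Month 12 (Table 9.1) | remainder of the V6 visit, then 0 days |
| SAEs, SADEs | to 30 days after last visit | 30 days (Table 9.1, Section 9.3) |
| Device deficiencies, incidents | to 30 days after last treatment or last visit, whichever is later | 30 days (Section 9.3) |

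An AE that starts during V6 is recordable, and if ongoing at exit it is followed until resolved or stable (Protocol 9.1.1). An ISR ongoing or appearing 30 days after the last visit goes to the sponsor's product surveillance, outside the protocol (Section 9.1.7).

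**2. What enters total volume**

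SAP 9.1 lists V1, V2 and V6 volumes, then the overall total, then the total by AE status, with no exclusion. SAP 7.4 also places Month 12 retreatment among the study treatments that need a prior pregnancy test. Against this, SAP 6.2 leaves retreatment out of study treatment. Inclusion of V6 is the natural reading, but it is not certain. AEs are treatment-emergent from the first treatment onward (SAP 9.3), with no separate retreatment period.

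**3. Effect on the table if V6 volume is included**

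The documents give no retreatment rate and no retreatment volume, so every input below is an assumption. Let v be the retreatment volume. If AE status is settled before retreatment,

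shift in (mean volume with AE − mean volume without AE) = v × [P(retreated | AE) − P(retreated | no AE)].

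| P(retreated): AE vs no AE | v = 0.5 mL | v = 1.0 mL | v = 1.5 mL |
|---|---|---|---|
| 0.5 vs 0.5 | 0 | 0 | 0 |
| 0.4 vs 0.6 | −0.1 | −0.2 | −0.3 |
| 0.3 vs 0.7 | −0.2 | −0.4 | −0.6 |
| 0.6 vs 0.4 | +0.1 | +0.2 | +0.3 |

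If retreatment is independent of AE status and of V1+V2 volume, the expected shift is zero but the added variance dilutes a volume–AE correlation by the factor s / √(s² + q(1−q)v²). Here s is the SD of V1+V2 volume and q the proportion retreated. With v = 1.0 mL, s = 0.4, 0.6 or 0.8 mL and q = 0.3, 0.5 or 0.8:

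- lowest: s = 0.4, q = 0.5: 0.4/√(0.16 + 0.25) = 0.62
- highest: s = 0.8, q = 0.8: 0.8/√(0.64 + 0.16) = 0.89

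Dependence on AE status is plausible. A subject who leaves the study because of an AE, which Protocol 8.2.1 allows, never reaches V6, and an earlier reaction may affect whether a subject accepts another injection.

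**The case against.** The strongest reply is that retreatment is an optional, free injection of a CE-marked product, offered after the Month 12 assessments, and that no planned efficacy endpoint depends on it. Limiting the diary to the two treatments under study is then a legitimate choice of scope. Table 14.3.4.4 is one descriptive table that drives no test or decision. This stands as to weight. It does not explain why the SAP should mix the two kinds of exposure in one total.

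Four stronger readings are tempting, and the documents do not support them.

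- A reader might infer that retreatment has no non-serious safety data at all. Events starting at V6 are recorded and followed (Protocol 9 and 9.1.1), any return to the site prompts questions about ISRs and AEs (Section 6.2.8), and device deficiencies and incidents run 30 days further (Section 9.3).
- A reader might infer that no later contact takes place. The Month 12 visit description, the visit schedule and parts of the diary instructions are not visible, and Protocol 7.1.6 mentions visits after Month 12. A later contact cannot be excluded, though it would not by itself change the diary scope in Section 9.1.7.
- A reader might take it as settled that V6 volume is in the table, or that this volume could have produced no collected AE. SAP 6.2 leaves the first open and the table shells are not visible. AEs at V6 and SAEs over the next 30 days contradict the second.
- A reader might put a number on the gap. With 30 to 60 subjects retreated and 18 to 36 touched up, the share of injection sessions without a diary or later non-serious AE collection runs from 30/(60+36+30) = 24% to 60/(60+18+60) = 43%. Both rates are assumptions, and the number retreated could be as low as zero.

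**Conclusion.** The visible text plans no non-serious AE or ISR collection after the V6 visit at which retreatment is given. On the natural reading of SAP 9.1, the retreatment volume nevertheless enters the total tabulated by AE status. That dilutes the comparison, and biases it in either direction if retreatment depends on AE status. A reversed comparison would need such dependence to be strong relative to the true difference, and nothing in the documents shows that it is.

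The size cannot be derived from the documents. The shifts of −0.6 to +0.3 mL and the dilution factors of 0.62 to 0.89 only illustrate the mechanism under assumed inputs. The effect falls mainly on the final analysis, because the interim is triggered when all subjects have completed Month 6 (SAP 10) and most retreatment would come later. The primary endpoint is not affected.

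**What to change.** 1. In SAP 9.1, restrict Table 14.3.4.4 to V1+V2 volume and to AEs with onset before retreatment. Report V6 retreatment exposure and any events after it separately. This costs nothing beyond SAP wording and a programming specification.
2. Reconcile SAP 6.2 with SAP 9.1 on whether retreatment is study treatment, and state which visits enter total volume wherever the term is used, including the scatter plot against FACE-Q (Figure 14.3.4.5).
3. Protocol 10.1 and SAP 6.2 name V5 as the end-of-study visit for completers, whereas Protocol Section 3 and SAP 3.3 place study exit at Month 12. Reconcile these, since the last visit closes AE collection in Table 9.1.
4. If the full visit schedule holds no contact after retreatment, align AE/ADE collection for retreated subjects with the 30-day SAE window already in Table 9.1, at the cost of a wording change and one contact per retreated subject. Otherwise, state that the study draws no non-serious safety conclusion about retreatment.

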### 9.2.2 Severity

The Investigator will determine the severity classification based on the following definitions, his/her experience in the use of dermal fillers and/or the subject’s description of the event. ISR severity is defined on the ISR 30-Day Diary.

The term “severe” is used to describe the intensity of an AE; the event itself could be of relatively minor clinical significance (e.g., ‘severe’ headache). This is not the same as “serious”. Seriousness of AEs is defined in *Section 9.1.2: Serious Adverse Events (SAE)*.

Severity will be assessed as:

- **Mild**            The AE does not interfere in a significant manner with the subject’s normal functioning level. It may be an annoyance.
- **Moderate**      The AE produces some impairment of function but not hazardous to health. It is uncomfortable and/or an embarrassment.
- **Severe**            The AE process significant impairment of functioning or incapacitation and/or it is a hazard to the subject.

If an AE changes in severity, the worst severity should be reported.

### 9.2.3 Causality

Relationship to a device refers to a determination of the relationship (if any) between an AE and the device. A causal relationship is present if a determination is made that there is a reasonable possibility that the AE may have been caused by the device.

An AE could be considered procedure-related when, in the judgment of the Investigator, it is reasonable to believe that the event is associated with the procedure, regardless of the relationship to the study device. Procedure-related causes that contribute to the occurrence of the event can be attributed to other products, surgical techniques, or medications required specifically for the procedure.

Relationship to the device or procedure must be determined by the Investigator and cannot be delegated to other study staff.

Causality will be assessed as:

**01 Not related:** relationship to the device or procedures can be excluded when:

Clinical Study Protocol: CMO-MA-FAS-0512

---

- the event is not a known side effect of the product category the device belongs to or of similar devices and procedures;
- the event has no temporal relationship with the use of the investigational device or the procedures.
- the serious event does not follow a known response pattern to the medical device (if the response pattern is previously known) and is biologically implausible;
- the discontinuation of medical device application or the reduction of the level of activation/exposure - when clinically feasible – and reintroduction of its use (or increase of the level of activation/exposure), do not impact on the serious event;
- the event involves a body-site or an organ not expected to be affected by the device or procedure;
- the serious event can be attributed to another cause (e.g. an underlying or concurrent illness/ clinical condition, an effect of another device, drug, treatment or other risk factors);
- the event does not depend on a false result given by the investigational device used for diagnosis, when applicable;
- harms to the subject are not clearly due to use error;
- in order to establish the non-relatedness, not all the criteria listed above might be met at the same time, depending on the type of device/procedures and the serious event.

**02 Unlikely:** the relationship with the use of the device seems not relevant and/or the event can be reasonably explained by another cause, but additional information may be obtained.

**03 Possible:** the relationship with the use of the investigational device is weak but cannot be ruled out completely. Alternative causes are also possible (e.g. an underlying or concurrent illness/ clinical condition or/and an effect of another device, drug or treatment). Cases where relatedness cannot be assessed or no information has been obtained should also be classified as possible.

**04 Probable:** the relationship with the use of the investigational device seems relevant and/or the event cannot reasonably be explained by another cause, but additional information may be obtained.

**05 Causal relationship:** the serious event is associated with the investigational device or with procedures beyond reasonable doubt when:

- the event is a known side effect of the product category the device belongs to or of similar devices and procedures;
- the event has a temporal relationship with investigational device use/application or procedures;
- the event involves a body-site or organ that the investigational device or procedures are applied to;
- the investigational device or procedures have an effect on;

Clinical Study Protocol: CMO-MA-FAS-0512

---

- the serious event follows a known response pattern to the medical device (if the response pattern is previously known);
- the discontinuation of medical device application (or reduction of the level of activation/exposure) and reintroduction of its use (or increase of the level of activation/exposure), impact on the serious event (when clinically feasible);
- other possible causes (e.g. an underlying or concurrent illness/ clinical condition or/and an effect of another device, drug or treatment) have been adequately ruled out;
- harm to the subject is due to error in use;
- the event depends on a false result given by the investigational device used for diagnosis, when applicable;
- in order to establish the relatedness, not all the criteria listed above might be met at the same time, depending on the type of device/procedures and the serious event.

#### 9.2.4 Pregnancy

If a female of childbearing potential becomes pregnant during the study, the Investigator will notify the Sponsor immediately by completing the Pregnancy Surveillance Form after the pregnancy is confirmed. The Investigator shall (1) instruct the subject to notify her physician of the presence of the medical device and (2) follow the progress of the pregnancy to term.

Pregnancy by itself will not be considered an AE or serious adverse event (SAE). Hospitalization for a normal delivery does not constitute an SAE. However, the occurrence of an adverse pregnancy outcome for the mother or child may constitute an AE or SAE, and these should be reported as described in *Section 9.2: Procedure for Reporting Adverse Events*. Allergan considers any abortion (spontaneous or not spontaneous) as a SAE and should be reported as described in *Section 9.3: Procedures for Reporting an SAE/SADE*.

#### 9.3 PROCEDURES FOR REPORTING AN SAE/SADE

The investigator is required to document AEs (non-serious and serious), device deficiencies, and incidents that occur during the duration of the study on the forms provided by Allergan.

All SAEs, device deficiencies, and incidents from consent to 30 days after the last treatment, or last study visit (whichever is later) are to be immediately (within 24 hours) reported to Allergan.

All subjects with a SAE, device deficiency, and incident must be followed up and the outcomes reported. The investigator is to supply Allergan and the EC with any additional requests for information.

An AE that continues beyond the end of the study final database lock will be followed independently from this study by the relevant Allergan safety department.

Clinical Study Protocol: CMO-MA-FAS-0512

---

Both the investigator and Allergan will comply with all Medical Device Reporting requirements.

## 10 STATISTICAL METHODS

### 10.1 GENERAL STATISTICAL CONSIDERATIONS

A brief summary of the general statistical analysis methods is provided below; full details will be provided in a separate Statistical Analysis Plan (SAP), which will be finalized prior to database lock.

Data will be summarized using descriptive statistics (number of observations (n), mean, standard deviation (SD), median, minimum, and maximum for continuous variables; and n and percent for categorical variables).

Baseline is defined as the latest assessment prior to any study treatments for each subject. End of study is the last clinical visit an enrolled subject has in this study. For subjects who complete this study, the end of study visit will be their V5 visit; for subjects who drop out early, they will be asked to come back for the last clinical visit for end of study data collection.

